2.2.3 Additional secondary endpoints

Additional secondary endpoints include:

- 1. CFBL in 3CS score at Weeks 4, 8, 12, 16, and 20
- 2. CFBL in the symptom score for individual cardinal symptoms of nasal blockage/obstruction/congestion, anterior/posterior nasal discharge, and facial pain/pressure at Weeks 4, 8, 12, 16, 20, and 24
- 3. CFBL in loss of smell score at Weeks 4, 8, 12, 16, 20, and 24, for all participants and for participants with baseline score ≥2
- 4. Improvement of ≥1 point, ≥2 points, and ≥3 points from baseline in 3CS score at Week 24
- 5. CFBL in SNOT-22 total score at Weeks 4, 8, 12, 16, and 20
- 6. CFBL in SNOT-22 subdomain scores at Weeks 4, 8, 12, 16, 20, and 24
- 7. Improvement of ≥8.9 and ≥12 from baseline in SNOT-22 total score at Week 24
- 8. CFBL in the Zinreich score of the bilateral anterior and posterior ethmoids at Week 20
- 9. Time to first rescue treatment requirement through Week 24
- 10. Sinonasal surgery requirement through Week 24
- 11. Rescue medication use through Week 24
- 12. Total systemic corticosteroid (SCS) dose prescribed through Week 24
- 13. Number of days on SCS through Week 24
- 16. CFBL in 36-Item short form health survey, version 2 (SF-36v2) physical health, mental health, and domain scores at Week 24
- 17. CFBL in EuroQoL 5-dimension, 5-level (EQ-5D-5L) score at Week 24
- 18. Improvement of ≥1 category and ≥2 categories in the severity of CRS-related symptoms, as indicated by the PGIS at Week 24
- 19. Overall change of "Very much better" or "Much better" in the CRS-related symptom severity as indicated by the PGIC at Week 24
- 20. CFBL in Medical Outcomes Study Sleep Scale (MOS Sleep-R) score at Week 24

21. CFBL in Work Productivity and Activity Impairment-Specific Health Problem (WPAI-SHP), version 2.0 at Weeks 4, 12, and 24

2.2.5 Safety endpoints

Safety endpoints include:

- 1. Treatment-emergent adverse events (TEAEs) and treatment-emergent serious adverse events (TESAEs) through Week 24.
- 2. Abnormal (clinically significant) laboratory values (hematology and chemistry) through Week 24.
- 3. Newly identified adverse endoscopic findings in middle meatus including epistaxis, mucosal erosion or ulceration, and perforation through Week 24.
- 4. Clinically significant increase of IOP through Week 24.
- 5. Newly identified or worsened cataract in one or both eyes by slit-lamp examination through Week 24.

For safety analysis incorporating the safety extension phase, the above safety endpoints will be summarized from Day 1 through Week 48 for the LYR-210 to LYR-210 and LYR-210 to Sham treatment sequences and from Safety Extension Day 1 through Week 48 for the Sham to LYR-210 treatment sequence.

3. Investigational Plan

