3.1 Study design

This global, multicenter study will be conducted in a randomized, controlled, parallel-group, participant-blinded fashion in approximately 180 symptomatic adult CRS participants who have failed previous medical management. Participants enrolled in the study will include participants who have accessible and intact middle meatus. The efficacy and safety of LYR-210 matrix (7500 µg) versus a control group receiving a sham procedure will be assessed on a background therapy of daily saline irrigation. Participants will be randomized 2:1 to either treatment with LYR-210 or to control.

The study will consist of 3 stages:

- Screening and run-in stage: 2-4 weeks before randomization and treatment procedure
- Treatment stage (LYR-210 or control): randomization and treatment procedure through 24 weeks
- Safety extension: Weeks 25 through 52

A safety extension phase after the Week 24 visit will involve crossover for all control participants and treatment participants will be re-randomized 1:1 to either sham or a second round of active treatment with follow-up through Week 52. The study design is depicted in **Figure 1**.

[figure not shown]
[figure not shown]

Figure 1. Study Design.

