3.5.7 Clinic follow-up visits

All participants will return to clinic for the scheduled follow up assessments at Weeks 8, 16, 20, 32, 40, 44, and 48. The end of study visit at Week 52 can be conducted as an in-office visit or over the phone. Assessments at these visits include a urine pregnancy test for women of childbearing potential, COVID-19 test, nasal endoscopy, 4CS, SNOT-22, concomitant medications/procedures, and AEs. PGIS will also be assessed at Week 8 and 16 visits. Plasma for PK testing will be collected for the previously selected 30 participants. Ocular examinations are required at Weeks 8, 16, 32, 40, and 48.

At the Week 20 and Week 44 visits, after the visit assessments, all participants will undergo a LYR-210 removal or sham removal procedure. Participants who receive LYR-210 will have bilateral matrix removal using standard surgical tools. Control participants will undergo a sham removal procedure to remain blinded.

If **spontaneous dislodgement of LYR-210** occurs before the scheduled Week 20 or Week 44 visit in participants who receive LYR-210, participants are required to call the study clinic immediately to report the event. If a participant experiences dislodgement of 1 LYR-210 matrix, the participant will continue in the treatment phase. Any participant who undergoes a dual dislodgement is required to complete the assessments scheduled for the Week 20/ET visit, and subsequently the Week 24/End of Treatment Phase (EOTP) visit within 25-31 days of the ET visit. Participants with dual dislodgement can be re-randomized in the extension phase.

Opacification of ethmoid sinuses will be assessed by CT scans obtained during screening (or using a historical CT scan taken within 1 month of screening) and within 7-14 days after Week 20/ET visit, unless medically contraindicated. Participants will be instructed to stop use of saline rinse approximately 24 hours prior to the scheduled sinus CT. Daily saline irrigation should then continue following the sinus CT. If a participant is experiencing or recovering from a cold, acute exacerbation of nasal allergy, or URTI at the timing of follow up CT, the CT should be performed 4 weeks after resolution of the AE. If a participant requires SCS or sinonasal surgery as rescue treatment, the follow-up CT should be performed before receiving the rescue treatment.

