3.5.9 Safety extension treatment

After completing the Week 24 visit, participants who completed the 24-week treatment phase (including participants with dual dislodgement) will continue into the safety extension phase. In this phase, all sham participants will undergo treatment with LYR-210. Treatment participants will be re-randomized 1:1 to undergo either a sham procedure or a second LYR-210 treatment procedure. Extension participants will not be required to repeat the Screening/run-in phase or CT scans but will otherwise repeat all the study visits and assessments for the 24-week treatment phase (see safety extension schedule of assessments in **Appendix 14.1**). Participants in the safety extension phase will undergo a second removal procedure at Week 44 and complete follow-up visits at Weeks 48 and 52. If medically warranted per the treating physician's discretion, early matrix removal may be performed at an unscheduled ET visit. Any participant who undergoes an ET visit is required to complete the assessments scheduled for the Week 44/ET visit, and subsequently the Week 48/End of Safety Extension Phase (EOSEP) visit within 25-31 days of the ET visit. ET participants are encouraged to continue completing ePRO assessments through Week 52.

Week 52 is the EOS visit for all participants who did not have early termination. The Week 52/EOS visit can be conducted either over the phone/virtual or as a clinic visit. Assessments include final ePROs (4CS and SNOT-22), concomitant medications/procedures, and AEs.

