7.6 Reporting adverse events

AEs are to be collected from the time a participant signs the informed consent form (ICF) until the completion of all follow-up visits. At each office or telephone/virtual visit during the study, AEs that have occurred since the previous office visit must be recorded. All participants will be evaluated for AEs or complications associated with the study procedure or the investigational product. The investigator will determine the severity and relationship of each event, as defined above. AEs observed during this study, regardless of severity or relationship to the study procedure or investigational product, will be recorded on the appropriate CRF.

Documentation of all new AEs or changes in previously reported AEs will be recorded. Preexisting diseases or conditions will not be reported as AEs unless there has been a substantial increase in severity or frequency of the problem, which cannot be attributed to the expected progression of the disease or condition.

The investigator will review the results of all clinical and laboratory tests as they become available. For each laboratory test result, the investigator will ascertain whether the result represents an abnormal (ie, clinically significant) CFBL for that individual participant. If this laboratory test result is determined to be a clinically significant abnormal CFBL for that participant, the value will be considered to constitute an AE.

All AEs will be coded using Medical Dictionary for Regulatory Activities (MedDRA) throughout the study.

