7.7 Reporting serious adverse events

7.7.1 Initial reports

All SAEs occurring from the time of informed consent until the completion of all follow-up visits must be reported to the sponsor or designee within 24 hours of the knowledge of the occurrence. After the completion of each follow-up visit, any SAE that the investigator considers related to study drug must be reported to the sponsor or designee.

To report the SAE, the investigator or designee must complete the AE form with the SAE information electronically in the electronic data capture (EDC) system for the study. When the form is completed, safety personnel will be notified electronically by the EDC system and will retrieve the form. If the event meets seriousness criteria and it is not possible to access the EDC system, the investigator or designee should send an email to the safety contact (as indicated by the sponsor) and fax/email the completed paper SAE form to the safety contact within 24 hours of awareness. When the EDC system becomes available, the SAE information must be entered as soon as possible.

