3.3.9 Study Drug Exposure (Up to Matrices Removal or Dislodgement) and Compliance
25

3.4 Efficacy Analysis	25
3.4.1 Primary Efficacy Endpoints	26
3.4.2 Key Secondary Efficacy Endpoints	28
3.4.3 Additional Secondary Efficacy Endpoints	29
3.4.5 Subgroups	31
3.5 Pharmacokinetic Assessment	32
3.6 Safety Analysis	32
3.6.1 Adverse Events (AEs).....	32
3.6.2 Clinical Laboratory Tests	33
3.6.3 Nasal Endoscopy.....	33
3.6.4 Vital Signs.....	33
3.6.5 Ophthalmologic Assessments.....	34
4 Analysis Timing.....	34
4.1 Interim Analysis	34
4.2 Final Analysis.....	34
5 Changes from Protocol	34
6 Programming Specifications	34
Appendix A: Reference	35
Appendix B: Laboratory Tests	36

LIST OF ABBREVIATIONS

Abbreviation	Definition
AE	Adverse event
AECRS	Acute exacerbation of CRS
ANCOVA	Analysis of covariance
AR	Allergic rhinitis
CFBL	Change from baseline
CI	Confidence interval
CMH	Cochran-Mantel-Haenszel
CRF	Case report form
CRS	Chronic Rhinosinusitis
CS	Cardinal symptoms
CSR	Clinical Study Report
CT	Computed tomography
eCRF	Electronic case report form
ePRO	Electronic patient-reported outcomes questionnaire
EQ-5D-5L	EuroQoL 5-dimension, 5-level
ET	Early termination
ICE	Intercurrent event
IOP	Intraocular pressure
IRC	Independent review committee
K-M	Kaplan-Meier
LS-means	Least squares means
MAR	Missing at random
MCID	Minimum clinically important difference
MedDRA	Medical Dictionary for Regulatory Activities
MF	Mometasone furoate
MI	Multiple imputation
MMRM	Mixed model with repeated measures
MNAR	Missing not at random
PGIC	Patient Global Impression of Change
PK	Pharmacokinetics
SAE	Serious adverse event
SAF	Safety analysis set
SAP	Statistical Analysis Plan
SCS	Systemic corticosteroids
SD	Standard deviation
SF-36v2	36-item short form health survey, version 2
SNOT-22	Sino-Nasal Outcome Test
TEAE	Treatment-emergent adverse event
TESAE	Treatment-emergent serious adverse event
WHO	World Health Organization

LIST OF KEY TERMS

Terms	Definitions
Initial Treatment Period	The 24 weeks of treatment after the first administration of study treatment and prior to second administration of study treatment in the extension period. Only this period will be evaluated for statistical comparisons between LYR-210 and sham for the efficacy.
Extension Treatment Period	Period after the first administration of study treatment in the extension period after completing initial 24-week of sham controlled treatment until the last day of study completion at Week 52 or early discontinuation.

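### The only extension safety summary with a stated window ends at Week 48 for every endpoint, while AEs and SAEs are collected to Week 52/EOS

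*Protocol*

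**What the plan says.** **Summary window.** Protocol 2.2.5 lists five safety endpoints: TEAEs/TESAEs, laboratory values, endoscopic findings, IOP and cataract. One sentence then sets the window for analyses that include the extension. For participants who start on LYR-210, the endpoints are "summarized from Day 1 through Week 48 for the LYR-210 to LYR-210 and LYR-210 to Sham treatment sequences". Controls who cross over get a later start but the same end, namely "from Safety Extension Day 1 through Week 48 for the Sham to LYR-210 treatment sequence". The synopsis says the same.

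**Length of the extension.** Protocol 3.1 gives "Safety extension: Weeks 25 through 52". The SAP's List of Key Terms defines the extension treatment period as running "until the last day of study completion at Week 52 or early discontinuation".

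**Collection.** Protocol 7.6 states that "AEs are to be collected from the time a participant signs the informed consent form (ICF) until the completion of all follow-up visits". Protocol 7.7.1 does the same for serious events: "All SAEs occurring from the time of informed consent until the completion of all follow-up visits must be reported". For the Week 52/EOS visit, Protocol 3.5.9 says "Assessments include final ePROs (4CS and SNOT-22), concomitant medications/procedures, and AEs".

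**Treatment emergence.** Protocol 7.1 counts any AE that starts or worsens from the procedure onward and sets no end. Footnote m of Protocol Table 5 assigns all AEs after the extension procedure to the extension arm, also with no end. SAP 3.6.1 instead limits TEAEs to 31 days after study treatment is discontinued, and then brackets a greater-than sign that says the opposite.

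**Scope of the SAP.** SAP section 1 restricts it to the first 24 weeks. SAP 4.2 leaves the details of the 52-week analysis to a separate SAP.

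**The concern.** One cut-off is applied to five endpoints that do not share a last assessment. In Protocol Table 5, laboratory tests, endoscopy and ocular examinations are last scheduled at Week 48, so that limit fits them. AEs are the only one of the five still assessed at Week 52.

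An AE in Week 50 is therefore collected, is treatment-emergent under Protocol 7.1, and is assigned to an extension arm under footnote m, yet it lies beyond the stated summary. The extension exists to characterise safety, including after a second LYR-210 course. The uncovered interval runs from about four to eight weeks after the second removal. SAEs and deaths matter most: the SAP 3.6.1 overview counts all serious AEs and all AEs leading to death without a treatment-emergent limit, but only for the 24-week period. Neither document states an equivalent count for Weeks 48-52.

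**Working it through.** The plan gives no figure on this point to reproduce. The check is calendar arithmetic on the stated windows.

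**Inputs**
- Second removal: Protocol 3.5.7 says "At the Week 20 and Week 44 visits, after the visit assessments, all participants will undergo a LYR-210 removal or sham removal procedure"; Table 5 places the Week 44 visit on extension Day 141±3, that is Day 138-144.
- Week 48 visit: 25-31 days after the Week 44 visit (Table 5).
- Week 52/EOS visit: 25-31 days after the Week 48 visit (Table 5).
- SAP TEAE limit: 31 days after discontinuation of study treatment, taken here as the scheduled removal (SAP 3.6.1).

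**Step 1: visit days.**
- Week 48: 138+25 = 163 to 144+31 = 175.
- Week 52: 163+25 = 188 to 175+31 = 206.

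**Step 2: interval beyond the stated summary.** Week 52 visit minus Week 48 visit = 25-31 days, nominally 4 weeks.

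**Step 3: share of each sequence's follow-up.**
- Sham to LYR-210 starts at extension Day 1. Weeks 25-52 are 28 weeks, and 4/28 = 14.3%.
- LYR-210 to LYR-210 and LYR-210 to Sham start at Day 1. 4/52 = 7.7%.

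**Step 4: how many TEAEs this affects under each definition.**
- Protocol 7.1 (no end): all 25-31 days are treatment-emergent and outside the summary.
- SAP 3.6.1 (removal + 31 days), if carried into the extension: the limit falls 31-31 = 0 to 31-25 = 6 days after the Week 48 visit, so the Week 48 cut loses only 0-6 days of TEAEs. The rest of the interval is not treatment-emergent. It runs from (25+25)-31 = 19 to (31+31)-31 = 31 days before the Week 52 visit.

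**Step 5: upper bound on exposure.** If all of about 180 participants enter and finish the extension, 180 × 4 = 720 participant-weeks lie beyond the cut. About 60 crossover and 60 re-randomised participants, 120 in all, would have received LYR-210 in the extension. Participants who end early reduce these figures.

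**The case against.** **Week 48 is a natural boundary.** Protocol 3.5.9 names the Week 48 visit as the end of the safety extension phase; Week 52 is a separate end-of-study contact that may be by telephone. The cut also mirrors the first course: removal at Week 20 and summaries through Week 24, then removal at Week 44 and summaries through Week 48. This stands as a plausible reason for the choice. But neither document gives it, and Protocol 3.1 and the SAP's key terms both run the extension to Week 52.

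**The SAP's 31-day limit nearly coincides with Week 48.** This also stands in part: under that limit almost no TEAEs are lost (Step 4). However, the limit sits in a SAP for the first 24 weeks, contradicts itself, and conflicts with Protocol 7.1. It also does nothing for SAEs and deaths that are counted regardless of treatment emergence.

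**A 52-week SAP is announced.** A reader might infer that late events fall outside every safety summary. The documents do not support that. SAP 4.2 defers the details of the 52-week analysis to a document not available here, and that document may cover Weeks 48-52. Equally, nothing available supersedes Protocol 2.2.5, and a later SAP that followed the protocol would inherit Week 48.

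**Nothing is lost.** Protocol 9.3.2 puts individual data in listings, and SAEs are reported to the sponsor until follow-up ends. That is correct, but Protocol 9.3.5 presents the safety endpoints as numbers and percentages by treatment group, which listings do not provide.

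**Conclusion.** The mismatch is real and small. The only extension safety summary with a stated window stops 25-31 days before AE collection does, and no available text says where AEs, SAEs and deaths from that interval are summarised. How many TEAEs are affected depends on an unresolved definition: the whole interval under Protocol 7.1, or 0-6 days under SAP 3.6.1 if it applies to the extension. All-SAE and death counts are exposed under either.

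The figures assume removal at the scheduled Week 44 visit and visits within their windows. The 14% applies only to Sham to LYR-210; the other two sequences lose about 8%. These are shares of follow-up time, not of events, and the documents give no late event rate from which to estimate a number of events. This is a gap in planned reporting, not in data collection, and it does not touch the Week 24 efficacy comparison.

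**What to change.** 1. In Protocol 2.2.5 and the synopsis, summarise AEs (TEAEs, TESAEs, all SAEs and deaths) through Week 52/EOS by treatment sequence, keeping the present start dates.
2. Keep Week 48 for the laboratory, endoscopy, IOP and cataract endpoints.
3. Carry both rules into the separate 52-week SAP.
4. Reconcile the TEAE window between Protocol 7.1 and SAP 3.6.1, and remove the contradictory bracket. Without this step, extending the cut-off to Week 52 would add few TEAEs under the SAP's definition. If a time limit is kept, show AEs after it in a separate row.

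The cost is wording in the protocol, its synopsis and the two SAPs. The data are already collected, and no visit or assessment changes.

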- 1. Treatment-emergent adverse events (TEAEs) and serious adverse events (TESAEs) through Week 24.
- 2. Abnormal (clinically significant) laboratory values (hematology and chemistry) through Week 24.
- 3. Newly identified adverse findings in middle meatus including epistaxis, mucosal erosion or ulceration, and perforation through Week 24.
- 4. Clinically significant increase of IOP through Week 24.
- 5. Newly identified or worsened cataract in 1 or both eyes by slitlamp examination through Week 24.

For safety analysis incorporating the safety extension phase, the above safety endpoints will be summarized from Day 1 through Week 48 for the LYR-210 to LYR-210 and LYR-210 to Sham treatment sequences and from Safety Extension Day 1 through Week 48 for the Sham to LYR-210 treatment sequence.

Key study assessments

- Cardinal symptoms (CS) questionnaire
- SNOT-22
- Work Productivity and Activity Impairment-Specific Health Problem (WPAI-SHP), version 2.0
- 36-Item short form health survey, version 2 (SF-36v2)
- EuroQoL 5-dimension, 5-level (EQ-5D-5L)
- Patient Global Impression of Severity (PGIS)
- Patient Global Impression of Change (PGIC)
- Medical Outcomes Study Sleep Scale (MOS Sleep-R)
- Endoscopic nasal examination
- Ocular examination (intraocular pressure [visual acuity [VA], IOP] and slit lamp)
- 3-D volumetric (CT) score
- Bilateral ethmoid Zinreich score
- Plasma pharmacokinetics (PK) (in ~30 participants only)
- Adverse events (AEs)

Week 24 Analysis

The data from the first 24-week period (Treatment Stage) will be locked (ie, CRFs will be frozen) when all participants complete the 24-week period and all data from this period is cleaned. Following database lock (ie, CRFs freeze), the data from this period will be analyzed according to the prespecified statistical analysis plan. The 24-week treatment analysis will be conducted to assess efficacy and safety during the first 24 weeks (i.e., Treatment Stage) excluding the endpoints measured after 24 weeks in the Safety Extension. Since all efficacy analyses comparing LYR-210 to sham are conducted based only on data through Week 24, no alpha adjustment is required as the information fraction at the 24-week analysis is 100%. There will be no additional statistical comparisons between LYR-210 vs sham beyond Week 24 timepoint. The efficacy data that are collected beyond Week 24 will be descriptively summarized without a formal statistical comparison.

Abbreviations and Acronyms

AE Adverse event

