3.5.4 Randomization and blinding

On Day 1, after confirmation of eligibility and baseline assessments, and before any treatment, participants will be randomized in a 2:1 ratio to receive LYR-210 treatment or control (sham procedure) with stratification based on region (North America vs Europe) and nasal polyp status (yes vs no). Randomization will be conducted using Interactive Response Technology (IRT) and treatment will be assigned according to a randomization scheme generated by an unblinded biostatistician. The person generating the randomization scheme will not be involved in the collection, review, and/or analysis of study data before database lock and unblinding of the database.

To maintain the participant blind to treatment assignment, each participant will wear an eye mask (ie, blindfold) and headphones at the time of the LYR-210 administration/sham procedure. Except for the cases of spontaneous matrix dislodgement, participants should remain blinded to their treatment assignment (LYR-210 or control) until the study is completed.

After Week 24, using IRT, control participants will be assigned to active treatment and treatment participants will be re-randomized 1:1 to either sham procedure or a second active treatment

procedure stratified by geographic region and nasal polyp status at baseline. Follow-up visits will continue through Week 52.

The sponsor will be blinded only to participants' initial study treatment assignments until database lock for the Week 24 primary analysis (initial randomized phase).

Due to the nature of the procedure, the treating investigator/surgeon will not be blinded to the treatment assignment. Efforts will be made to keep the study coordinator and other study staff blinded.

Breaking the blind to the participant is expressly forbidden except in the event of spontaneous dislodgment of LYR-210, or a medical emergency where the identity of the treatment assignment must be known to properly treat the participant. If breaking the blind is required because of a medical emergency, decision to unblind lies solely with the investigator. In all cases where the blind is broken to the participant, the investigator must record the date and reason for breaking the blind. The unblinding should be noted in the participant's eCRF.

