3.5.10 Discontinuation of Study Participants

Each subject is free to discontinue from the study at any time, for any reason, and without penalty or loss of benefit. Participation in the study treatment may be discontinued for any of the following reasons:

• Occurrence of any medical condition or circumstance that exposes the subject to substantial risk and/or does not allow the subject to adhere to the requirements of the protocol, including early removal of LYR-210

- Any serious AE (SAE, Section 7.2), clinically significant AE, severe laboratory abnormality, intercurrent illness, pregnancy, or other medical condition that indicates to the Investigator that continued participation is not in the best interest of the subject.
- Subject's decision to withdraw
- If deviations to the use of prohibited medications occur after randomization and study treatment, the Investigator in consultation with the Sponsor and Sponsor's medical monitor will decide on a case-by-case basis whether the subject may continue in the study based on the time the prohibited medication was administered and its pharmacology.
- Subject's failure to comply with protocol requirements or study related procedures.
- Termination of the study by the Sponsor or a regulatory authority that has provided approval to proceed.

Subjects who withdraw or are withdrawn from the study treatment will be requested to return to the clinic for the assessments and procedures scheduled for the end of treatment visit and the safety follow up visits (Section 3.5.9). The Investigator or study staff will document the reason(s) for subject discontinuation on the Case Report form (CRF) and notify the IRB/EC as required by their Institution's procedures.

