3.7.13 Sinonasal surgery (actual or planned) for CRS

For participants who have a surgery or have a scheduled date for sinonasal surgery as rescue for CRS, the reason (worsening signs and/or symptoms during the study), the date the surgery was indicated, expected or actual surgery date, and the type and outcome of surgery will be recorded in the eCRF. Types of sinonasal surgery include, but are not limited to, functional endoscopic sinus surgery (FESS), balloon sinuplasty, turbinate reduction, septoplasty or polypectomy, or any endoscopic procedure that results in sinonasal tissue removal.

If the surgery is to be performed during the study treatment period, the study treatment will be discontinued and all procedures/assessments for the ET and EOTP visits will be completed prior to the surgery. The participant will be discontinued from the study.

If the surgery is to be performed during the safety extension phase, the study treatment will be discontinued and all procedures/assessments for the ET and EOSEP visits will be completed prior to the surgery. The participant will be discontinued from the study.

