7.8 Exposure in utero

If a participant becomes pregnant during the treatment phase, the matrix will be removed (or sham removal) and the participant will continue study follow-up through Week 24. The participant will not continue to the safety extension phase. However, the investigator must continue to follow the participant until the completion of the pregnancy, including the outcome and the condition of the newborn at 8 weeks postpartum (if applicable).

If a participant becomes pregnant during the safety extension phase, the matrix will be removed (or sham removal) and the participant will continue study follow-up through Week 52. Additionally, the investigator must follow the participant for safety until the completion of the pregnancy, including the outcome and the condition of the newborn at 8 weeks postpartum (if applicable).

A pregnancy is not considered to be an AE or SAE; however, it must be reported within 24 hours of knowledge of the event. Sponsor or designee will then provide the Exposure In Utero (EIU) form to the investigator/site for completion and return.

The pregnancy should be followed until the outcome of the pregnancy, whenever possible. Once the outcome of the pregnancy is known, the EIU form should be completed and faxed/emailed to sponsor or designee. If the outcome of the pregnancy meets the criteria for immediate classification as an SAE (ie, postpartum complication, spontaneous abortion, stillbirth, neonatal death, or congenital anomaly), the investigator should follow the procedures for reporting an SAE.

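### The Day 1 to Week 48 safety summary groups LYR-210 participants by an assignment made after Week 24, so recipients who never enter the extension are in none of its named sequences

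*Protocol*

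**What the plan says.** For the safety analysis that takes in the extension, Protocol 2.2.5 (and, in the same terms, the synopsis) names three treatment sequences and gives each a window. The five safety endpoints are "summarized from Day 1 through Week 48 for the LYR-210 to LYR-210 and LYR-210 to Sham treatment sequences". Participants who start on sham have a shorter window, which runs "from Safety Extension Day 1 through Week 48 for the Sham to LYR-210 treatment sequence". No other group is named.

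The sequence is settled late. Protocol 3.5.4: "After Week 24, using IRT, control participants will be assigned to active treatment and treatment participants will be re-randomized 1:1". Protocol 3.5.9 says that "participants who completed the 24-week treatment phase (including participants with dual dislodgement) will continue into the safety extension phase".

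Several routes lead out before that point:
- Protocol 3.5.10 allows discontinuation for a serious or clinically significant adverse event (AE) "that indicates to the Investigator that continued participation is not in the best interest of the subject", and at the participant's own wish.
- Protocol 3.7.13, on sinonasal surgery during the treatment period: "The participant will be discontinued from the study".
- Protocol 7.8, on pregnancy in the treatment phase: "The participant will not continue to the safety extension phase".
- SAP 3.1.2.2 also provides for participants who finish the treatment stage without going on to the extension.

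All of these people are in the safety analysis set if they were successfully treated on Day 1 (Protocol 9.3.1, SAP 3.2.1). Safety results are to be given as numbers and percentages of participants (Protocol 9.3.5). Details for the 52-week data are left to a separate SAP that is not among the supplied documents (SAP 4.2).

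**The concern.** The clock for the two LYR-210 sequences starts on Day 1, but membership is decided about 24 weeks later. That is grouping by a future event. Anyone placed in LYR-210 to LYR-210 or LYR-210 to Sham must have stayed in the study long enough to be re-assigned, so the first half of their window is selected for people who stayed.

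Two things follow. LYR-210 recipients who left, or who finished Week 24 and did not continue, have no place in the summary. And the events most likely to matter for long-term tolerability, deaths and AEs that end participation, cannot be seen in Weeks 1 to 24 of either LYR-210 column.

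The windows also differ. The third sequence is counted over about 24 weeks and the other two over 48, with percentages of participants as the stated measure. At stake is whether the protocol's long-term summary, which is also where repeat implantation is described, gives a fair picture of everyone exposed.

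**Working it through.** **1. The plan's own figure.** The documents give no figure for the 48-week safety summary. The nearest is the planned arm sizes, 60 control and 120 LYR-210, with 95% power at effect size 0.57, 2-sided alpha 0.05 (SAP 2.2.4). Normal approximation:

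power = Φ(0.57 × √(60 × 120 / 180) − 1.96) = Φ(3.605 − 1.96) = Φ(1.645) = 0.950

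This reproduces the stated 95% (0.948 with the noncentral t). It confirms only that 120 is the number of LYR-210 participants who could feed the two sequences; it has no bearing on the safety point.

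**2. Timing of counting against timing of grouping.**

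| Sequence | Counting starts | Sequence fixed | Window counted before grouping |
|---|---|---|---|
| LYR-210 to LYR-210 | Day 1 | after Week 24 | 24 of 48 weeks |
| LYR-210 to Sham | Day 1 | after Week 24 | 24 of 48 weeks |
| Sham to LYR-210 | Safety Extension Day 1 | after Week 24 | none |

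24 / 48 = 50%. In that half, the number of deaths and participation-ending AEs in the LYR-210 columns is zero by construction, whatever the true rate. This needs no assumption about rates. The 50% holds on the nominal schedule; participants with dual dislodgement may have a shorter first part, because their Week 24/EOTP visit follows the early-termination visit by 25 to 31 days (Protocol 3.5.7).

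**3. How many people are in no named sequence.** The supplied text gives no exit rate. Let d be the share of the 120 who do not enter the extension (assumed range 5% to 20%).

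In no sequence = 120 × d; in the two LYR-210 sequences = 120 × (1 − d), split 1:1.

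| d (assumed) | In no sequence | In the two sequences | Per sequence |
|---|---|---|---|
| 5% | 6 | 114 | 57 |
| 10% | 12 | 108 | 54 |
| 15% | 18 | 102 | 51 |
| 20% | 24 | 96 | 48 |

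**4. Unequal windows.** Nominal follow-up is 48 weeks in two columns and 24 in the third, a ratio of 48 / 24 = 2. A percentage of participants with an event depends on the time at risk, and no follow-up time or exposure adjustment is specified.

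**5. A second attribution rule.** Protocol Appendix 14.1, Table 5, note m, attributes AEs arising after the extension procedure to the extension arm. Section 2.2.5 instead pools both periods under one sequence label for participants first given LYR-210. The documents do not say how the two rules fit together.

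**The case against.** The strongest reply is that this rests on silence. Section 2.2.5 sets time windows by sequence; it fixes no denominator and does not forbid a further column, and the layout belongs to a 52-week SAP that is not supplied. Note m even points towards extension-period attribution. This stands in part: the separate SAP could add the missing group. But nothing supplied says that it will, and the protocol's stated rule, followed as written, names three sequences and no more.

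Second, early leavers' events are reported. The Week 24 safety summary covers the whole safety set by treatment received and includes AEs leading to discontinuation, with differences, odds ratios and confidence intervals (SAP 3.6.1). This stands. The events are not lost from the trial report, and first-implant tolerability against concurrent sham is unaffected.

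Third, a reader might infer that, because half the window is blind to these events, the sequence columns show about half of the true 48-week incidence. The documents do not support that. It needs an exit rate they do not give and a constant risk across both halves, which is hard to defend for LYR-210 to Sham, where there is no implant in the second half. It also concerns AEs ending participation, which is not one of the five listed endpoints. For those five, first-half events in everyone who is re-randomized are counted.

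Fourth, a reader might infer that every AE that ends treatment disappears. It does not. After early matrix removal a participant still has the Week 20/ET and Week 24/EOTP visits (Protocol 3.5.8), and those with dual dislodgement may be re-randomized (3.5.7). Such AEs can appear in a sequence column. The documents do not settle which other early-termination participants may enter.

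Fifth, the unequal windows are stated openly, each starts at first LYR-210 exposure, and no formal safety test is planned (Protocol 9.3.5). That is correct, so nothing is disguised; but side-by-side percentages still need follow-up time to be read.

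**Conclusion.** The concern holds for the long-term summary only. As written, the Day 1 to Week 48 figures leave out LYR-210 recipients who never enter the extension. In 24 of the 48 weeks counted, the two LYR-210 columns cannot show a death or an AE that ended participation. Those structural facts rest only on the protocol's text and nominal schedule. The number of people affected is unknown: 6 to 24 of about 120 if 5% to 20% do not enter, which is an assumption. No figure for understated incidence can be given from the documents. The 48-week and 24-week percentages are not directly comparable without follow-up time. The primary efficacy analysis and the Week 24 safety conclusions are not touched.

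**What to change.** In Protocol 2.2.5, the synopsis and the separate 52-week SAP:

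- Add a summary of all participants who received LYR-210, from first LYR-210 insertion to last follow-up. Include those never re-randomized, and sham crossovers from their own insertion.
- Report exposure-adjusted incidence (events per participant-time actually followed) beside numbers and percentages.
- Show the three sequence columns from Safety Extension Day 1, as is already planned for Sham to LYR-210, so that all share one starting point and the same nominal window.
- Reconcile this wording with note m to Table 5 in Appendix 14.1, so that one rule governs which column an AE after the extension procedure enters.

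The cost is wording and one more column, with one more denominator to explain. No new data are needed.
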